8.7.4 Efficacy Analysis Plots

The following plots will be provided for Safety and Efficacy Analysis Set, respectively:

- Waterfall plots of the best percentage change in tumor size (i.e., maximum tumor reduction, or minimum increase in the absence of any reduction) (Gillesp et al 2012)
- Swim lane plot for responders

Confidential Page 28 of 30

8.7.5 Subgroup Analyses of Efficacy

Summaries of BOR, ORR, DOR, DCR, PFS, OS, and the waterfall plot will be reported in the following subgroups:

- HCC patients, non-HCC and PD-1/PD-L1 refractory patients, and non-HCC and PD-1/PD-L1 naïve patients
- by drug manufacturing process
- by age groups (age $< 55 \text{ vs} \ge 55$, age $< 65 \text{ vs age} \ge 65$, age $< 75 \text{ vs age} \ge 75$)
- by race group including at least 5 subjects and grouping together all categories with < 5 subjects as "Other"
- by tumor burden (sum of baseline target lesions by investigator assessment) \leq 50 mm vs > 50 mm

8.7.6 Progression-Free Survival

Progression-free survival (PFS) is defined as the interval from the date of first dose of investigational agent until the earliest date of PD per RECIST 1.1 or death due to any cause within 90 days (i.e., 12 weeks+6 days) of last tumor assessment (if no progression is documented). If a patient transitioned to a new anti-cancer therapy, any time point assessment(s) and death(s) that happened after that will be disregarded.

The primary analysis will be performed ignoring transient PDs, using the same definition of transient PDs as in Section 8.7.1. Thus, the terminating event will be a non-transient PD or death, whichever occurs first. Patients who did not experience a non-transient PD or death will be censored on the date of last evaluable tumor assessment, the date of the last evaluable assessment without any assessment in the following 90 days and then followed by PD or death, or the last evaluable assessment performed before initiation of new anti-cancer therapy (if applicable), whichever comes earlier.

The alternative (sensitivity) analysis will be performed for terminating event of death or first observed time-point PD, whichever occurs first. Censoring will be on the date of last evaluable tumor assessment, the date of the last evaluable assessment without any assessment in the following 90 days and then followed by PD or death, or the last evaluable assessment performed before initiation of new anti-cancer therapy (if applicable), whichever occurs first.

PFS will be reported in months. Median PFS will be provided (estimated using K-M estimate, with 95% CI) and Kaplan-Meier curves of PFS will be plotted.

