6.2.1.2 Secondary Endpoints

- Objective response rate, (ORR), defined as the percentage of subjects having CR or PR, as determined by radiographic disease assessments per RECIST 1.1.
- Disease control rate (DCR) will include subjects that have best overall response (BOR) of CR, PR and SD for at least 12 weeks.
- Progression-free survival (PFS), defined as the interval from the date of first dose of investigational agent until the earliest date of disease progression, as determined by investigator assessment of objective radiographic disease assessments per RECIST 1,1, or death due to any cause if occurring sooner than progression.
- Duration of response, (DOR), defined as the interval from the date measurement criteria are met for CR or PR (whichever is first recorded) until the earliest date of disease progression, as determined by investigator assessment of objective radiographic disease assessments per RECIST 1.1, or death due to any cause if occurring sooner than progression. Only subjects who achieve an initial response will be evaluated for DOR.
- Overall survival (OS), defined as the interval from the date of first dose of investigational agent until the date of death.
- The pharmacologically active dose of AGEN1884, determined through clinical signs of drug activity, surrogate markers, and pharmacodynamic studies, including but not limited to the presence of irAEs.

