6.4.2.1 Progression-Free Survival

Subjects who are alive and have not progressed at the time of analysis will be censored at the time of the last clinical assessment noted to be free of progression. The distribution of PFS times, including median PFS time and PFS rates, will be estimated in a pooled manner and by each dose level and study cohort using the Kaplan-Meier method with 95% confidence intervals. Dates of progression will be based on RECIST 1.1.

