8.7.2 Duration of Response

Duration of response (DOR) will be analyzed only for subjects who responded to the study treatment. DOR is defined as the time from first observation of CR or PR which was subsequently confirmed until the first time of disease progression or death by any cause within 90 days (i.e., 12 weeks+6 days) of last tumor assessment. All assessments performed before initiation of a new anti-cancer therapy will considered for evaluation of DOR. If a patient transitioned to a new anti-cancer therapy, any time point assessment(s) and death(s) that happened after that will be disregarded. Similar to evaluation of BOR, in the primary analysis any transient time-point PD(s) will be disregarded for determination of DOR when followed by confirmed objective response or durable stable disease, as defined in Section 8.7.1. In the alternative (sensitivity) analysis, DOR will be counted using the date of first observed PD, whether transient or not.

The starting event for DOR will be the date of the first objective response. The terminating event will be the date of PD or death within 90 days (i.e., 12 weeks+6 days) of the last tumor assessment, whichever occurs first. The censoring event will be the earliest of the dates of last evaluable assessment, last evaluable assessment performed before initiation of new anti-cancer therapy (if applicable), or last evaluable assessment without any assessment in the following 90 days and then followed by PD or death.

DOR will be reported in months and summarized by quartiles estimated from Kaplan-Meier curve, as well as Kaplan-Meier estimates at 6, 9, 12, 18 months. Number and percent of censored and non-censored observations and a plot Kaplan-Meier curve will be provided.

In addition, duration of observation of DOR (whether censored or not) will be summarized as "Observed DOR". The shortest and longest observations will be provided with censoring indicator.

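### The SAP counts deaths in PFS and DOR only within 90 days of the last scan; the protocol sets no limit, no planned analysis gives the protocol's PFS, and SAP 5.1 declares no change

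*SAP*

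**What the plan says.** **Protocol.** Section 6.2.1.2 ends PFS and DOR at the earliest radiographic progression, "or death due to any cause if occurring sooner than progression". It sets no limit on the time between the last scan and the death. For PFS, section 6.4.2.1 adds: "Subjects who are alive and have not progressed at the time of analysis will be censored". Section 6.4.2.4 summarises DOR by median, minimum, maximum and number of subjects, and gives no censoring rule.

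**SAP, endpoint list.** Section 4.5 repeats the protocol definitions, again without a limit.

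**SAP, analysis sections.**
- Section 8.7.6 counts for PFS a "death due to any cause within 90 days (i.e., 12 weeks+6 days) of last tumor assessment (if no progression is documented". Among its censoring dates is "the date of the last evaluable assessment without any assessment in the following 90 days and then followed by PD or death".
- After a new anti-cancer therapy, "any time point assessment(s) and death(s) that happened after that will be disregarded".
- On progression, "The primary analysis will be performed ignoring transient PDs". The sensitivity analysis goes back to the first observed progression, but its censoring sentence repeats the 90-day and new-therapy rules.
- Section 8.7.2 does the same for DOR: "The terminating event will be the date of PD or death within 90 days (i.e., 12 weeks+6 days) of the last tumor assessment". It also starts DOR from a response that was later confirmed.

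**SAP, declared changes.** Section 5.1, which summarises changes from the protocol's planned analysis, has one entry: None.

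**The concern.** A reader with the protocol in hand will take the reported PFS to be time to first progression or death. Under the SAP, a subject who stops having scans and dies more than 90 days after the last one is not an event and is censored back at that scan. That subject's known survival between the scan and the death also leaves the risk set. Whether a death counts therefore depends on how long after the last scan it occurs: early deaths stay in as events, and late ones are removed retrospectively.

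These deaths are known to the trial. Survival follow-up collects them for up to 2 years (protocol 5.1.5), the SAP death summary tabulates them (8.6.2), and OS counts them (8.7.7). The report would therefore show PFS and DOR that differ from the protocol definition, say that nothing had changed, and give no protocol-defined PFS to compare with.

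**Working it through.** **1. The stated limit.** 12 × 7 + 6 = 90 days, so the SAP's own equivalence is right.

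**2. Side-by-side reading for PFS.**

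| Rule | Protocol 6.2.1.2 / 6.4.2.1 | SAP 8.7.6 primary | SAP 8.7.6 sensitivity |
|---|---|---|---|
| Progression | first | non-transient only | first observed |
| Death more than 90 days after last scan | event | censored at scan | censored at scan |
| Death after new therapy | event | disregarded | disregarded |
| Who is censored | alive and progression-free only | also the two death rows above | also the two death rows above |

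The sensitivity paragraph mentions death without a limit. However, the section's opening definition still applies, and the paragraph's own censoring sentence repeats the 90-day gap. The Efficacy Analysis Set runs (8.7) and the subgroups (8.7.5) set no other definition. Neither SAP column matches the protocol column.

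**3. One subject.** Last scan on study day 84 without progression, no new therapy, death on study day 180. The gap is 180 − 84 = 96 days. With the SAP's 30.4375 days per month:
- protocol: event at 180 / 30.4375 = 5.9 months;
- SAP, primary and sensitivity: censored at 84 / 30.4375 = 2.8 months.

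**4. How many deaths could be affected (assumed inputs).** The documents give no event counts or survival assumptions. Suppose a subject stops scans without progression, receives no new therapy, and has exponential survival with median m months from the last scan. The share of deaths after day 90 is 2^(−2.957/m), where 90 / 30.4375 = 2.957.

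| m (months) | 1 | 2 | 3 | 6 | 12 |
|---|---|---|---|---|---|
| Share after day 90 | 13% | 36% | 50% | 71% | 84% |

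Over this range of m, the deaths moved from event to censored among 60 Phase 2 subjects are:
- 3 such subjects: 0.4 to 2.5;
- 6 such subjects: 0.8 to 5.1;
- 12 such subjects: 1.5 to 10.1.

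**5. Effect on the Kaplan-Meier estimates (simulation, assumed inputs).** There were 400,000 subjects per scenario. A share of 5%, 10% or 20% (3, 6 or 12 of 60) has its last scan at day 43 or 85 with equal odds, and then dies with median m as above. The rest have exponential progression with median 3, 6 or 12 months, read at 6-weekly scans from day 43. There is no other censoring. This makes 3 × 3 × 5 = 45 scenarios. SAP minus protocol PFS rate, over days 182, 273 and 365:

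| Affected | Range (percentage points) |
|---|---|
| 3 of 60 | −2.4 to +1.0 |
| 6 of 60 | −4.7 to +1.8 |
| 12 of 60 | −9.5 to +3.4 |

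Median PFS is the same in 36 of 45 scenarios and moves by 3 to 42 days in the other 9. Two cases with 6 of 60 affected show why the sign is not fixed:
- Others progress quickly (median 3 months) and m = 6: −3.3 points at day 182, because the SAP drops subjects who were outliving the rest.
- Others progress slowly (median 12 months) and m = 3: +1.8 points at day 365, because the SAP mainly drops events.

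For scale, the standard error of a 50% rate with 60 subjects is √(0.25/60) = 6.5 points.

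A separate run with n = 60, 10–30% of subjects stopping scans at baseline, Week 6 or Week 12, median progression of 2.5 or 4 months, and median death 3 or 6 months after the last scan moved about 2 to 9 deaths. The median was unchanged in 11 of 12 scenarios (4.5 versus 4.1 months in the other), and the 6-month rate was about 1 to 7 points lower under the SAP.

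All of these figures are for PFS. None was computed for DOR.

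**The case against.** **The protocol allows it.** Protocol section 6 lets the SAP modify the planned analyses and requires an amendment only for major changes to the primary endpoint. PFS and DOR are secondary, single-arm and descriptive, with no inferential sample size, and OS counts every death. All of this stands and it limits the weight of the point. It does not make the entry None in SAP 5.1 accurate, and it does not reconcile SAP 4.5 with 8.7.

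**Few subjects will be affected.** A subject must have a gap of more than 90 days without a scan and then die without new therapy, although protocol 5.1.2, 5.7.1 and Table 10 call for continued scans. The largest shift in the table needs 12 of 60 such subjects with 12-month median survival while the rest progress at a 3-month median, and nothing in the documents supports that. SAP 8.7.6 also lists the median and the curve, not landmark rates; the rates come from protocol 6.4.2.1. This too stands, and it is why the size is put at a few points.

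**Stronger readings that the documents do not support.**
- A reader might infer that the rule inflates PFS. It turns events into censored times but also drops the follow-up before them, so the estimate can move either way.
- A reader might say that the primary censoring sentence contradicts itself, because "Patients who did not experience a non-transient PD or death will be censored on the date of last evaluable tumor assessment" opens a list that includes a gap followed by progression or death. It is poorly drafted. For deaths, the opening definition resolves it. For late progression, the parallel DOR and sensitivity wording points to censoring. A clarification is enough.
- A reader might call 90 days too short for 12-weekly scans, since Table 10's ±7-day window allows 84 + 7 + 7 = 98 days between on-time scans. That matters for progression only if late progression is censored. The 3-day margin that the SAP uses elsewhere (39 = 42 − 3; 81 = 84 − 3) gives 84 + 3 + 3 = 90, which fits the rule.
- A reader might want the protocol definition made the main analysis. That is a preference; the documents do not require it.
- A reader might carry the alive-and-progression-free censoring rule over to DOR. The protocol states it for PFS only.

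**Conclusion.** The point holds as a difference between the protocol and the SAP that the SAP does not declare. It rests on the text, not on the simulations: a death 96 days after the last scan is a PFS event under protocol 6.2.1.2, 6.4.2.1 and SAP 4.5, and is censored in every planned PFS analysis, while SAP 5.1 reports no change. The same 90-day limit applies to DOR.

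The documents do not determine the numerical effect. Under the assumptions above, median PFS is usually unchanged, and with 3 to 6 of 60 subjects affected, PFS rates shift between −4.7 and +1.8 points, less than one standard error of 6.5 points. No direction of bias is claimed. Because the sign is not fixed, a reader cannot correct for the rule without seeing the protocol-defined estimate. This should be corrected before the final analysis; it does not threaten the primary safety and PK objectives.

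**What to change.** (a) **PFS.** Add one supplementary analysis on the protocol definition. The event is the first RECIST 1.1 progression or death from any cause whenever it occurs, including after new therapy, and only subjects alive and progression-free are censored. Keep the existing primary and sensitivity analyses.

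**DOR.** Add a supplementary run that ends at first progression or any-cause death with no 90-day limit, following protocol 6.2.1.2. State its censoring rule in the SAP, because the protocol gives none.

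(b) **Declaration.** Replace None in SAP 5.1 with the actual departures: the 90-day death limit, missed-assessment censoring, new-therapy censoring, the handling of transient progression, and DOR counted from a confirmed response. Align SAP 4.5 with 8.7.

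(c) **Wording.** Redraft the primary PFS censoring sentence to match the parallel DOR and sensitivity wording, so that it says plainly whether a progression found after a gap of more than 90 days is an event.

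**Cost.** One added derivation each for PFS and DOR, using death dates already collected for OS, plus SAP text. No new data are needed. The report will carry estimates that may differ slightly between versions and will need a sentence to explain why.

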4.5 Secondary Endpoints

- Objective response rate, (ORR), defined as the percentage of subjects having complete response (CR) or partial response (PR), as determined by radiographic disease assessments per RECIST 1.1.
- Disease control rate (DCR) will include subjects that have best overall response (BOR) of CR, PR and stable disease (SD) for at least 12 weeks.
- Progression-free survival (PFS), defined as the interval from the date of first dose of investigational agent until the earliest date of disease progression (PD), as determined by investigator assessment of objective radiographic disease assessments per RECIST 1.1, or death due to any cause if occurring sooner than progression.
- Duration of response, (DOR), defined as the interval from the date measurement criteria are met for CR or PR (whichever is first recorded) until the earliest date of disease progression, as determined by investigator assessment of objective radiographic disease assessments per RECIST 1.1, or death due to any cause if occurring sooner than progression. Only subjects who achieve an initial response will be evaluated for DOR.
- Overall survival (OS), defined as the interval from the date of first dose of investigational agent until the date of death.
- The pharmacologically active dose of AGEN1884, determined through clinical signs of drug activity, surrogate markers, or pharmacodynamic studies, including but not limited to the presence of immune-related adverse events.

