5 PLANNED ANALYSIS

5.1 Summary of Changes to the Planned Statistical Analysis Described in the Protocol

None.

Confidential Page 12 of 30

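### The SAP's primary PFS and DOR skip transient progressions, and its DCR admits stable disease after progression, against the stated definitions and with no change declared in SAP 5.1

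*SAP*

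**What the plan says.** **PFS.** Protocol 6.2.1.2 has PFS "defined as the interval from the date of first dose of investigational agent until the earliest date of disease progression" by RECIST 1.1, or death if sooner. Protocol 6.4.2.1 adds: "Dates of progression will be based on RECIST 1.1". SAP 4.5 keeps the rule: "until the earliest date of disease progression (PD), as determined by investigator assessment of objective radiographic disease assessments per RECIST 1.1". SAP 8.7.6 opens in the same way, "until the earliest date of PD per RECIST 1.1 or death due to any cause within 90 days" of the last tumor assessment. Its next paragraph then states: "The primary analysis will be performed ignoring transient PDs, using the same definition of transient PDs as in Section 8.7.1". First observed PD becomes the alternative (sensitivity) analysis.

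**DOR.** Protocol 6.2.1.2 and SAP 4.5 again end at the earliest progression or death. SAP 8.7.2 disregards transient PDs in the primary analysis and uses first PD only for sensitivity.

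**DCR.** Protocol 6.2.1.2 counts "best overall response (BOR) of CR, PR and SD for at least 12 weeks". SAP 8.7.3 adds subjects with durable SD after a PD. Its alternative version omits them.

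**Transient PD.** Under SAP 8.7.1 this is a PD later followed by a confirmed response or by durable SD. Durable SD needs at least two SD, PR or CR assessments 39 or more days apart and no new PD within 84 days, counted from the last transient PD.

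**Declaration.** SAP 5.1, headed "Summary of Changes to the Planned Statistical Analysis Described in the Protocol", contains the single entry None.

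**The concern.** The headline PFS and DOR would not follow the definitions printed in the protocol and in the SAP's own endpoint section, and SAP 5.1 would not tell the reader.

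The direction is mostly favourable. Each affected subject's PFS is later or unchanged. DCR can only rise or stay the same. Median DOR can move either way, because the rule can also add responders. OS is untouched.

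Whether a PD counts is settled by later scans, read by investigators in an open-label, single-arm study. Those scans exist only for some subjects: those treated beyond progression (Protocol 3.7), those scanned at the end-of-treatment and 90-day visits (Table 10), and those who stopped drug for another reason. For the last group, Protocol 5.7.1 continues scans past the first PD, whereas 5.1.2 ends them at PD.

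**Working it through.** The plan states no power, event count or effect size that bears on this point, so there is no figure to reproduce. The check sets the texts side by side and then applies the SAP rule to assumed scan sequences.

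**1. Texts compared**

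| Endpoint | Protocol 6.2.1.2 and SAP 4.5 | SAP section 8.7 primary | SAP section 8.7 sensitivity |
|---|---|---|---|
| PFS | earliest PD or death | first non-transient PD or death | first PD or death |
| DOR | earliest PD or death | transient PDs disregarded | first PD |
| DCR | CR, PR, or SD for 12 weeks | adds durable SD after PD | no SD after PD |

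In each row the sensitivity version carries the protocol's progression rule. Appendix E of the protocol defines PD at a time point and asks for no confirmation.

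**2. Scan days (Table 10).** Cycle 3 Day 1 = 1 + 42 = Day 43. Cycle 4 Day 15 = 1 + 63 + 14 = Day 78. Then every 6 weeks: Days 120, 162, 204. Months = days / 30.4375 (SAP 8.1).

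**3. One PD ignored.** Assume PD on Day 43 and SD on Days 78 and 120.
- Gap between SD scans: 120 − 78 = 42 days, at least 39.
- First-PD PFS: 43 / 30.4375 = 1.4 months.
- SAP primary PFS: at least 120 / 30.4375 = 3.9 months.
- The 84-day window ends on Day 43 + 84 = 127, but the SD scans cover only 120 − 43 = 77 days. The subject qualifies if the condition means that no PD was recorded in the window. SAP 8.7.1 does not say whether the full 84 days must be observed.

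**4. A repeated PD ignored.** Assume PD on Days 78 and 120, and SD on Days 162 and 204.
- SD gap: 204 − 162 = 42 days. Window end: 120 + 84 = Day 204, which is reached, so this case qualifies on either reading.
- PFS moves from 78 / 30.4375 = 2.6 to at least 204 / 30.4375 = 6.7 months.
- The two PDs are 120 − 78 = 42 days apart. Because the clock runs from the last transient PD, the rule puts no limit on how many can be skipped.

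**5. DOR at first PD.** Assume PD on Day 43 and PR on Days 78 and 120. The SAP's primary best-response rule makes this a confirmed responder from Day 78. Ending DOR at the first PD gives 43 − 78 + 1 = −34 days. First-PD DOR is therefore defined only if its responders also come from the first-PD best-response algorithm.

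**6. Effect per affected subject.** With no earlier censoring, one subject is 1/60 = 1.7, 1/40 = 2.5 or 1/20 = 5.0 points on the PFS curve between the old and new dates. DCR gains the same for a subject counted only through the rule, and nothing for one already counted.

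**7. Median PFS.** At n = 60, take two affected subjects whose PDs fall at one scan. If the median is the first time the curve reaches 0.5 or below, it moves only when 30 or 31 events have accrued by that scan. If it is the midpoint whenever the curve sits exactly at 0.5, 32 events also moves it. SAP 8.7.6 does not name the convention.

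A simulation gives a rough range. It assumes exponential PFS with true medians of 1.5 to 4 months, the scan days above, no other censoring, and affected subjects chosen at random and censored two scans later. The mean of the estimated medians rises by under 0.1 month with 1 of 60 affected, 0.1–0.3 with 3 and 0.3–0.7 with 6. With 3 affected, the median moves at all in about 10–23% of runs under the first convention and about 18–33% under the second. The numbers affected are assumptions.

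**The case against.** **Permission.** Protocol section 6 lets the SAP modify the plans and asks for an amendment only for major changes to the primary endpoint. This stands. A reader might infer that an amendment is missing, but the documents do not support that, because PFS, DOR and DCR are secondary. Permission to change does not make an entry of None correct.

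**Both versions will be produced.** First-PD versions of best response, DOR, DCR and PFS are all pre-specified, and SAP 8.7 states the rule openly. Nothing is hidden or lost. What remains is which result is labelled primary and whether it matches its definition.

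**Confirmed progression in Protocol 3.5.** That section defines progression as confirmed by a second consecutive assessment at least 6 weeks later. It sits under discontinuation of therapy, not in the endpoint definitions, and the SAP rule can skip even a PD repeated 6 weeks later (step 4). It is context, not a rescue.

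**DCR.** A reader might infer that about 6 weeks of SD replaces the protocol's 12. That comparison is not like for like: 42 days is a scan-to-scan span, the protocol does not say where its 12 weeks begin, and durable SD has its own 84-day clock. The supportable criticism is that this clock restarts at the last transient PD.

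**ORR.** A reader might extend the contradiction to best response and ORR. The protocol is silent on responses after PD, so there the SAP rule is permissive but contradicts nothing.

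**Conclusion.** The point stands as an internal contradiction and an undeclared change, and it should be fixed. Protocol 6.2.1.2, SAP 4.5 and the first sentence of SAP 8.7.6 cannot be reconciled with the primary PFS rule. The same holds for DOR between SAP 4.5 and 8.7.2, and DCR admits a category that its definition does not mention.

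The overall size cannot be stated, because no transient-PD rate is given. The per-subject figures (1.7, 2.5 or 5.0 points) follow from the planned numbers. The worked PFS shifts rest on assumed scan sequences, and the Day 43 case also on the looser reading of the 84-day condition. Any shift in the median rests on assumed rates and on the median convention. The endpoints are secondary and descriptive, so the harm is to how preliminary efficacy is read, not to a test.

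**What to change.** - Make the pre-specified first-PD analysis primary for PFS, DOR and DCR. Take the DOR responders and the DCR responses from the secondary (first-PD) best-response algorithm, so that no response starts after the PD that ends it. State that this algorithm also allows at most one intervening NE or SD before a PR is confirmed and drops SD criterion ii.
- Report the transient-PD version as a sensitivity analysis, with the number of subjects affected and the number of PDs ignored. State whether the 84 days must be observed in full.
- List in SAP 5.1 the departures that remain: deaths counted only within 90 days of the last scan; the rule that, once a new anti-cancer therapy starts, "any time point assessment(s) and death(s) that happened after that will be disregarded"; and the 81-day SD window against the protocol's 12 weeks (84 days).
- If the sponsor keeps the current order, it must correct SAP 4.5 and the opening of 8.7.6 and declare the change in 5.1.

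The cost is SAP wording only, since the algorithms already stand in SAP 8.7.1 to 8.7.3 and 8.7.6. The downside is that headline PFS and DCR may look slightly less favourable.

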For patients who did not fulfill requirements for BOR of CR or PR as described above, BOR of SD is defined, in the primary analysis, as i) initial time point assessment(s) of SD, PR, CR without PD at a minimum interval of 39 days (6 weeks-3 days), disregarding NE assessments and/or ii) unconfirmed PR or CR any time at initial evaluation, without PD at a minimum interval of 39 days and/or iii) durable SD following transient PD: at least 2 assessment(s) of SD, PR, CR (ignoring intercurrent NE assessments) at least 39 days (6 weeks-3 days) apart and without new PD within 84 days, counting time from the last transient PD assessment. Subjects who have a response of PR or CR with no subsequent tumor assessments will be assigned a BOR of SD and will be flagged in listings. In the secondary analysis, BOR evaluation of SD is only considered based on only criterion i) above. For BOR of SD without confirmation, the stable disease must meet the criterion of minimum time of 39 days.

For patients with time point assessment(s) of PD, excluding any transient PDs (PD followed by confirmed objective response or durable SD) and who do not satisfy criteria for BOR of CR, PR, and SD described above, the BOR assessments in the primary analysis will be PD. In the secondary analysis, a similar definition will be used but without excluding transient PDs.

Finally, BOR of NE will be assigned where there are either no evaluable time point assessments at all or first time point assessment(s) of SD was before minimum interval of 39 days without evaluable assessments preformed after 39 days.

The objective response rate (ORR) is the percentage of subjects with a BOR of PR or CR (i.e., objective response). The analysis of ORR will include confirmed responses and unconfirmed responses for both primary and alternative analyses. Subjects with missing tumor response status assessment will be counted as non-response (that is, subjects without any follow-up assessment) will be counted in the denominator for ORR.

BOR and ORR will be listed for Safety Analysis Set as available using primary and alternative definitions. For confirmed response, duration of response will be listed (see Section 8.7.2). The listings of time-point response will include assessments of target lesion, non-target lesions, and

Confidential Page 27 of 30

new lesion data, as well as percentage change from baseline in the sum of diameters of target lesions.

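### The 90-day scan-gap limit for DOR and alternative PFS is shorter than the 98-day gap that the protocol's own ±7-day window allows with 12-weekly imaging, and whether it covers PD needs stating

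*SAP*

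**What the plan says.** **DOR (SAP 8.7.2).** DOR is the "time from first observation of CR or PR which was subsequently confirmed" until PD or death, with a 90-day limit from the last tumor assessment attached to the death. One of the censoring dates is the "last evaluable assessment without any assessment in the following 90 days and then followed by PD or death". Results are given as Kaplan-Meier quartiles, "as well as Kaplan-Meier estimates at 6, 9, 12, 18 months".

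**PFS (SAP 8.7.6).** The definition counts "death due to any cause within 90 days (i.e., 12 weeks+6 days) of last tumor assessment". Two analyses follow.

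- Primary: the event is a non-transient PD or death. The censoring list opens with "Patients who did not experience a non-transient PD or death will be censored on the date of last evaluable tumor assessment" and goes on to include the gap clause, "the date of the last evaluable assessment without any assessment in the following 90 days and then followed by PD or death".
- Alternative: the event is death or the first PD of any kind. The list opens with "Censoring will be on the date of last evaluable tumor assessment", without restricting it to event-free patients, and repeats the gap clause.

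**Imaging (protocol 3.1, 5.7.1 and Table 10, footnote d).** Scans are due at Weeks 6 and 12. After that they are 6-weekly for the 3- and 6-week treatment schedules and 12-weekly for the 12-week schedule. Table 10 puts ±2 days on Week 12 and ±7 days on the later assessments, on those after discontinuation, and on the visits 28 and 90 days after the last dose. Section 5.7.1 keeps scans on their original calendar when dosing is delayed.

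**Protocol censoring (6.4.2.1).** Only subjects alive and free of progression are censored. There is no gap rule.

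**The concern.** A gap rule is meant to catch missed scans, where the date of progression is too uncertain to use. If its limit is shorter than the longest gap the schedule permits, it also removes events from subjects who missed nothing. Whether a PD counts can then depend on a scan falling a few days late inside its allowed window. Each lost PD becomes a censored time about 12 weeks earlier, which tends to lengthen the estimates.

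The limit appears to have been built on a different tolerance. The SAP's other cut-offs assume 3 days: "without PD at a minimum interval of 39 days (6 weeks-3 days" in SAP 8.7.1, and 81 days (12 weeks less 3 days) in SAP 8.7.3. For imaging after Week 12 the protocol states ±3 days only in section 3.7, for 6-weekly scans in treatment beyond PD.

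The primary PFS wording adds a second problem. A list meant for patients without a PD or death includes a case that ends in PD or death, so two programmers could produce different curves.

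**Working it through.** **1. The SAP's figure.** 12 × 7 + 6 = 90 days, as stated. It equals 84 + 3 + 3, the longest 12-weekly gap under a ±3-day window. Likewise 42 − 3 = 39 and 84 − 3 = 81.

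**2. Longest compliant gap.** Nominal interval + days the first scan may be early + days the second may be late:

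| Pair of scans | Sum | Longest gap (days) |
|---|---|---|
| 12-weekly, both ±7 | 84 + 7 + 7 | 98 |
| Week 12 (±2) to Week 24 (±7) | 84 + 2 + 7 | 93 |
| On-time scan, then one at +7 | 84 + 0 + 7 | 91 |
| 6-weekly, both ±7 | 42 + 7 + 7 | 56 |
| 28-day to 90-day visit after last dose | 62 + 7 + 7 | 76 |

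The first three exceed 90 and the last two do not.

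**3. Share of compliant 12-weekly gaps over 90 days.** Count the day pairs with 84 + d2 − d1 > 90.

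- Uniform attendance over ±7: 36/225 = 16.0%. Week 12 to Week 24: 6/75 = 8.0%.
- Attendance clustered on the due date (truncated normal, SD 2, 3 or 4 days): 1.0%, 5.5% or 9.3%.
- If windows were ±3: 0/49.
- If the +1-day interval convention in SAP 8.1 applies to the limit: 45/225 = 20.0% (uniform).
- With a limit of 98 days: 0/225.

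The attendance patterns are assumptions; the documents give none.

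**4. Who is exposed.** Subjects on the 12-week treatment schedule, after Week 12. If protocol 3.5 (12-weekly after stopping therapy) governs rather than 5.7.1 (6-weekly or disease-specific), also subjects off treatment without PD, but only after the 90-day Final Safety Visit, because the scans before it are at most 76 days apart. Neither number is given.

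**5. Size if PDs are censored.** Simulated with exponential event times, no missed scans, and scans at Days 43 and 78, then every 84 days (42 where imaging is 6-weekly). Shifts are in percentage points.

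*DOR, confirmed responders, assumed true median 6 to 12 months:*

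| Imaging | Attendance | 6 mo | 9 mo | 12 mo | 18 mo |
|---|---|---|---|---|---|
| All 12-weekly (worst case) | uniform | +0.8 to +3.0 | +2.5 to +5.0 | +3.0 to +3.9 | +1.7 to +4.5 |
| All 12-weekly | SD 3 | +0.1 to +1.6 across all four | | | |
| A quarter 12-weekly | uniform | +0.2 to +1.0 for 6 to 12 mo | | | +0.4 to +2.5 |
| A quarter 12-weekly | SD 3 | 0 to +0.4 for 6 to 12 mo | | | +0.1 to +0.8 |

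Median DOR, all 12-weekly, moves 0 to 8 days, or 34 to 56 days where the 50% point falls between two scans.

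*Alternative PFS, assumed true median 3, 4 and 6 months, all 12-weekly:* 12-month PFS rises by 1.0, 1.8 and 2.8 points (uniform) or 0.3, 0.5 and 0.8 (SD 3). Median PFS moved at most 1 day in 35 of 36 scenarios and 28 days in the other.

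*Sampling error for comparison:* the binomial SE of 12-month PFS at n = 60 is 3.5 to 5.8 points. For DOR at a true 50%, √(0.25/n) gives about 22, 16 and 11 points for 5, 10 and 20 responders (assumed numbers).

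Deaths lost to the limit cannot be sized from the documents.

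**The case against.** **The event sentences put no gap limit on PD.** Alternative PFS ends at death or first PD without qualification, and in DOR the 90 days can be read as attached to death alone. A reader might therefore infer that no PD is ever censored or, in the other direction, that the SAP plainly censors PDs in all three analyses. Neither is settled. Censoring PDs is the better reading for DOR and alternative PFS, because the gap clause names PD and would not need to if only deaths were meant. For primary PFS the list's opening words point the other way.

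**The ±7 days is a visit window.** It matches the dosing window, and footnote d gives no separate one for imaging. That is fair, but Table 10 applies it to the column that schedules the scans, and no other window is stated for 12-weekly imaging.

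**Few subjects may be exposed.** This stands. The 12-week schedule is agreed individually with the medical monitor, and nobody may be on it. It would also be wrong to infer that everyone who stops treatment before PD is exposed, for the reasons in step 4. The upper simulated figures assume that all subjects are imaged 12-weekly with uniform attendance.

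**The planned PFS summary hardly moves.** This stands too: SAP 8.7.6 reports the median and the curve, not a 12-month rate.

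**Conclusion.** The limit is wrong as written, and the consequence is minor. On the natural reading of the censoring lists for DOR and alternative PFS, an in-window PD can be discarded because 90 days is shorter than the 98 days that Table 10 permits. The calendar arithmetic is certain. That PDs are covered is the better reading, not the only one. The bias is upward for late DOR and the later part of the alternative PFS curve. Its size depends on the share of 12-weekly imaging and on attendance within the window, neither of which is in the documents. Even the worst-case shifts, up to 5.0 points for DOR and 2.8 points for 12-month PFS, are below the sampling errors shown.

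A reader might infer that the efficacy conclusions are materially biased or that a test is compromised. The documents do not support that: these are descriptive secondary endpoints, and the sample size is not based on inference.

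Primary PFS is internally inconsistent. Read literally, it loses no PDs to the gap rule. The primary and alternative analyses would then differ in the gap rule as well as in transient PDs, so comparing them would not isolate the effect of transient PDs.

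**What to change.** 1. In SAP 8.7.2 and 8.7.6, raise the gap limit and the limit on deaths from 90 to 98 days (99 if the SAP 8.1 convention applies, and say so). Apply it either to 12-weekly imaging only or to all subjects. The second is simpler but always tolerates one missed 6-weekly scan, since 2 × 42 + 14 = 98. The present 90 days already tolerates one in 189 of 225 day pairs (225 − 36).
2. State for DOR, primary PFS and alternative PFS whether the gap rule covers PD as well as death. Use the same rule in both PFS analyses so that they differ only in transient PDs.
3. Optionally, add one PFS and one DOR sensitivity run without a gap limit, stating whether censoring at new therapy is kept. Some events would then be dated later and less precisely, which tends to lengthen both endpoints.

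The cost is one constant, a few sentences and at most two extra runs.

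Separate housekeeping, which does not affect the severity: SAP 5.1 reports no changes from the protocol. Protocol section 6 lets the SAP modify the plan, but the death limit and gap rule should be listed there. The off-treatment imaging intervals in protocol 3.5 and 5.7.1 must be reconciled, because they determine who is exposed.
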